5.2. General Methods

As described in Section 3.4, in this study ‘**treatment arm**’ refers to one of the following:

- Arm A = avelumab alone;
- Arm B = avelumab plus PLD;
- Arm C = PLD alone.

Endpoints will be summarized based on the analysis sets described in Table 4 by treatment arm, unless otherwise specified.

5.2.1. Data handling after the cut-off date

Data after the cut-off date may not undergo the cleaning process and will not be displayed in any listings or used for summary statistics, statistical analyses or imputations.

5.2.2. Pooling of centers

In order to provide overall estimates of treatment effects, data will be pooled across centers. The ‘center’ factor will not be considered in statistical models or for subgroup analyses due to the high number of participating centers in contrast to the anticipated small number of patients randomized at each center.

5.2.3. Presentation of continuous and qualitative variables

Continuous variables will be summarized using descriptive statistics ie, number of non-missing values and number of missing values [ie, n (missing)], mean, median, standard deviation (SD), minimum, maximum and first and third quartile (Q1 and Q3).

Qualitative variables will be summarized by frequency counts and percentages. Unless otherwise specified, the calculation of proportions will include the missing category. Therefore counts of missing observations will be included in the denominator and presented as a separate category.

In case the analysis refers only to certain visits, percentages will be based on the number of patients still present in the study at that visit, unless otherwise specified.

5.2.4. Definition of study day

Start day of study treatment is the day of the first dose of study treatment.

The study day for assessments occurring on or after the start of study treatment (eg, adverse event onset, tumor measurement) will be calculated as:

$$\text{Study day} = \text{Date of the assessment/event} - \text{start of study treatment} + 1.$$

The study day for assessments occurring prior to the first dose of study treatment (eg, baseline characteristics, medical history) will be negative and calculated as:

Study day = Date of the assessment/event - start of study treatment.

The study day will be displayed in all relevant data listings.

5.2.5. Definition of start of new anti-cancer drug therapy

Start date of new anti-cancer drug therapy is used to determine the end of the on-treatment period (see Section 5.2.7).

The start date of new anti-cancer drug therapy is the earliest start date of anti-cancer drug therapy recorded in the 'Follow-up Cancer Therapy' eCRF pages that is after the first dose of study treatment. When the start date of anti-cancer drug therapy is missing or partially missing, the imputation rules described in Section 5.3.3.4 should be applied using only data from the 'Follow-up Cancer Therapy' eCRF pages.

5.2.6. Definition of start of new anti-cancer therapy

Start date of new anti-cancer therapy (drug, radiation, surgery) is used for censoring in efficacy analyses (see Section 6.1.2 and Section 6.2.2).

The start date of new anti-cancer therapy is the earliest date after randomization amongst the following:

- Start date of anti-cancer drug therapy recorded in the 'Follow-up Cancer Therapy' eCRF pages
- Start date of radiation therapy recorded in 'Concomitant Radiation Therapy', and 'Follow-up Radiation Therapy' eCRF pages with 'Treatment Intent' = 'Curative in intent'
- Surgery date recorded in 'Follow-up Surgery' eCRF pages when 'Surgery Outcome' = 'Resected' or 'Partially Resected'.

When the start date of anti-cancer therapy is missing or partially missing, the imputation rules described in Section 5.3.3.4 should be applied using 'Follow-up Cancer Therapy', 'Concomitant Radiation Therapy', 'Follow-up Radiation Therapy', and 'Follow-up Surgery' eCRF pages.

5.2.7. Definition of on-treatment period

Safety endpoints will be summarized based on the on-treatment period unless otherwise specified.

On-treatment period is defined as the time from the first dose of study treatment through minimum (30 days + last dose of study treatment, start day of new anti-cancer drug therapy – 1 day).

Safety data collected outside the on-treatment period as described above will be listed and flagged in listings but will not be summarized.

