8.2. Reporting Period

For SAEs, the active reporting period to Pfizer or its designated representative begins from the time that the subject provides informed consent, which is obtained prior to the subject's participation in the study, ie, prior to undergoing any study-related procedure and/or receiving investigational product, through and including 90 calendar days after the last administration of the study treatment.

SAEs occurring to a subject after the active reporting period has ended should be reported to the sponsor if the investigator becomes aware of them; at a minimum, all SAEs that the investigator believes have at least a reasonable possibility of being related to study treatment are to be reported to the sponsor.

AEs (serious and non-serious) should be recorded on the case report form (CRF) from the time the subject has taken at least 1 dose of study treatment through 90 calendar days after the last administration of the study treatment.

If a patient begins a new anticancer therapy, the AE reporting period for nonserious AEs ends at the time the new treatment is started. Death must be reported if it occurs during the SAE reporting period after the last dose of study treatment, irrespective of any intervening treatment.

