6.6.1. Adverse events

Treatment-emergent adverse events (TEAEs) are those events with onset dates occurring during the on-treatment period for the first time, or if the worsening of an event is during the on-treatment period as defined in Section 3.5.1.

All analyses described will be based on TEAEs (started during the on-treatment period) if not otherwise specified. The AE listings will include all AEs (whether treatment-emergent or not). AEs outside the on-treatment period will be flagged in the listings.

- **Related Adverse Events:** adverse events with relationship to study treatment (as recorded on the AE eCRF page, Relationship with study treatment = Related) reported by the investigator and those of unknown relationship (ie, no answer to the question ‘Relationship with study treatment’). Related AEs are those related to any study drug (ie, at least one of the study drugs).
- **Serious Adverse Events (SAE):** serious adverse events (as recorded on the AE eCRF page, Serious Adverse Event = Yes).
- **Adverse Events Leading to Dose Reduction:** adverse events leading to dose reduction of study treatment (as recorded on the AE eCRF page, Action taken with study treatment = Dose reduced).
- **Adverse Events Leading to Interruption of Study Treatment:** adverse events leading to interruption of study treatment (as recorded on the AE eCRF page, Action taken with study treatment = Drug interrupted). The eCRF does not allow for a clear separation between interruption of an infusion and delays of administration for a parenteral drug as both are recorded using the same term on the eCRF (“Drug interrupted”). IRRs will be excluded in the analysis of AEs leading to Drug Interruption in case they only led to an interruption of the infusion.
- **Adverse Events Leading to Permanent Treatment Discontinuation:** adverse events leading to permanent discontinuation of study treatment (as recorded on the AE eCRF page, Action taken with study treatment = Drug withdrawn).
- **Adverse Events Leading to Death:** adverse event leading to death (as recorded on the AE eCRF page, Outcome = Fatal, as well as AEs of Grade 5).
- **Immune-related Adverse Events (irAE):** irAEs (as identified according to the methodology outlined in Appendix 1 for a pre-specified search list of MedDRA PTs, documented in the Safety Review Plan and finalized for analysis of the current studies data prior to DB lock)

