9. APPENDICES

Appendix 1. Immune-Related Adverse Events

The MedDRA PTs and clusters for irAEs are defined in the Safety Review Plan (SRP) for avelumab.

Immune-related AEs (irAEs) will be programmatically identified as outlined in Table 16. This case definition is hierarchical, ie, each step is only checked for patients and events that have already met the prior step.

Table 16. Case Definition for irAEs

Step	Selection Criteria	Additional Notes
1	Event selected based on a list of pre-specified MedDRA PTs within clusters. These are included in the SRP as Tier1 events (Immune-mediated xxxx). If AE matches the list then it is in for the next step	
2	AE onset during 1 st study drug administration or anytime thereafter through 90 days after last dose of study treatment.	This is regardless of start of new anti-cancer drug therapy and regardless of TEAE classifications
3	Answer in the AE eCRF page to ‘Was another treatment given because of the occurrence of the event’ is ‘YES’	
4	AE treated with corticosteroids or other immunosuppressant therapy. For endocrinopathies only: AE required hormone replacement	Look in the conmed pages for AE identifiers that match the AEs from Step 3. For each of such AEs if A) OR B) below are met then the AE is in for the next step A) conmed ATC code is in (H02A, H02B, H02C, D07, A01AC, S01BA, S01BB, L04AA, L04AB, L04AC, L04AD, L04AX) and AE PT is in any of the irAE clusters. B) conmed ATC code is in (H03A, H03B) and AE PT is in one of the irAE clusters associated with “Immune-mediated endocrinopathies”

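### SAEs, and non-serious AEs before new anticancer therapy, arising 31 to 90 days after the last dose are collected but only listed, not tabulated by arm, apart from immune-related AEs and the all-deaths summary

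*SAP*

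**What the plan says.** **Collection (Protocol 8.2).** SAEs are actively reported "through and including 90 calendar days after the last administration of the study treatment". Serious and non-serious AEs go on the CRF from the first dose "of study treatment through 90 calendar days after the last administration of the study treatment". There is one early stop, which applies to non-serious events only: "If a patient begins a new anticancer therapy, the AE reporting period for nonserious AEs ends at the time the new treatment is started".

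**Summary window (SAP 5.2.7).** The on-treatment period runs from the first dose to the earlier of 30 days after the last dose or the day before new anti-cancer drug therapy. The default can be overridden: "Safety endpoints will be summarized based on the on-treatment period unless otherwise specified". Outside the window: "Safety data collected outside the on-treatment period as described above will be listed and flagged in listings but will not be summarized".

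**AE and SAE tables (SAP 6.6.1 and 6.6.3).** For AEs: "All analyses described will be based on TEAEs (started during the on-treatment period) if not otherwise specified". Section 6.6.3 tabulates treatment-emergent SAEs and sends later ones to a flagged listing.

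**Where the SAP departs from the default.** Appendix 1 (Table 16, Step 2) accepts immune-related AEs (irAEs) with onset at the first administration "or anytime thereafter through 90 days after last dose of study treatment", whatever their treatment-emergent status and whether or not new drug therapy has begun. Section 6.6.2 tabulates all deaths by arm with reason, alongside deaths within 30 days.

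**The concern.** Evaluating the overall safety profile against PLD is a secondary objective (Protocol 2.1). SAP 6.6.4 plans between-arm risk differences for irAEs, infusion-related reactions and common AEs. An SAE or Grade 3 or higher AE that begins on day 45 and is not classed as immune-related enters none of those comparisons. A reader could find it only by counting through a listing, without a denominator or a breakdown by preferred term.

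The SAP also mixes windows. The overall AE summary in Section 6.6.1.1 sets irAEs, which qualify up to 90 days, beside SAEs and other AEs that stop at 30 days at the latest. If 90 days is relevant for one class of toxicity, a supporting view of the serious events over the same period is a natural request.

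**Working it through.** The plan states no figure on this point, so there is nothing to reproduce. The check is arithmetic on the two windows.

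**Inputs**
- Collection window: 90 days after the last dose (Protocol 8.2).
- Summary window: 30 days after the last dose, or to the day before new anti-cancer drug therapy if sooner (SAP 5.2.7).
- Non-serious AE collection ends at new anticancer therapy; SAE collection does not (Protocol 8.2).
- Let t be the post-dose day on which new therapy starts. The documents give no distribution for t, so the values below are illustrative assumptions. The protocol's new anticancer therapy and the SAP's new anti-cancer drug therapy are taken to start on the same day.

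**Formulas**
- Days summarised: S = min(30, t − 1), or 30 with no new therapy.
- SAE share untabulated: (90 − S)/90.
- Non-serious share untabulated: (C − S)/C, with C = min(90, t), or 90 with no new therapy.

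**Base case, no new therapy:** (90 − 30)/90 = 60/90 = 66.7%, for both SAEs and non-serious AEs.

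| t (day) | S | SAE days untabulated | Non-serious days untabulated |
|---|---|---|---|
| 10 | 9 | 81/90 = 90.0% | 1/10 = 10.0% |
| 20 | 19 | 71/90 = 78.9% | 1/20 = 5.0% |
| 30 | 29 | 61/90 = 67.8% | 1/30 = 3.3% |
| 31 | 30 | 60/90 = 66.7% | 1/31 = 3.2% |
| 45 | 30 | 60/90 = 66.7% | 15/45 = 33.3% |
| 60 | 30 | 60/90 = 66.7% | 30/60 = 50.0% |
| 75 | 30 | 60/90 = 66.7% | 45/75 = 60.0% |
| 90 or none | 30 | 60/90 = 66.7% | 60/90 = 66.7% |

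For SAEs, two thirds is a floor: the share rises when new therapy starts before day 31. For non-serious AEs it is the largest value in the table. When new therapy starts by day 31, at most the start day itself is lost.

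**Which events are affected.** irAEs are not, on the reading that Appendix 1 is the override that Section 5.2.7 allows. Infusion-related reactions are not, because Appendix 2 requires onset on the infusion day or the day after. Deaths are counted by reason in Section 6.6.2, but the table of AEs leading to death by system organ class (SOC) and preferred term (PT) in Section 6.6.1.1 covers treatment-emergent events only. What remains is late non-irAE SAEs, and late non-irAE non-serious AEs with onset before new therapy.

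**The case against.** The case against has several parts, and most of it narrows the point.

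- **The SAP does summarise some late data.** Read alone, the closing sentence of Section 5.2.7 invites the inference that nothing after day 30 may be tabulated, or that late fatal toxicity disappears. The documents do not support either. The section allows exceptions, and the death table has no day limit. Its reasons include treatment toxicity and unrelated AE. Only the SOC/PT detail for late fatal AEs is missing.
- **Late immune toxicity is covered.** Qualifying therapy under Appendix 1 includes immunosuppressants other than steroids and, for endocrinopathies, hormone replacement. Medical review may add cases the algorithm misses. This stands.
- **The new-therapy cut-off partly mirrors the protocol.** A reader might infer that the SAP closes the window sooner in whichever arm switches sooner. For non-serious AEs that is the protocol's collection rule. For SAEs it is the SAP's choice, but the documents give no time to new therapy by arm, so neither size nor direction of an imbalance can be stated.
- **There is no contradiction.** Protocol 9.5 puts the emphasis on treatment-emergent AEs without giving a day limit, and promises no 90-day tables. The amendment history ties the 90-day change to a regulator's request about the reporting period, not about tables.

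None of this supplies a by-arm count of late non-irAE SAEs or Grade 3 or higher AEs. Listing them keeps the data visible but does not make the arms comparable.

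**Conclusion.** The point holds as a gap between collection and tabulation, of low severity. SAEs, and non-serious AEs before new anticancer therapy, with onset on days 31 to 90 are collected but have no by-arm table, apart from irAEs and the all-deaths summary. For SAEs the gap also opens earlier than day 31 when new drug therapy starts earlier.

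The size is 60 of 90 post-dose calendar days for a patient without new therapy. It would be tempting to read this as two thirds of late events going uncounted. The documents do not support that: they give no late event counts, and the share depends on when new therapy starts and on whether the event is serious. The conclusion rests on the Appendix 1 window governing the irAE tables and on the SAP text as written, with no further tables specified elsewhere.

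**What to change.** Keep the 30-day treatment-emergent tables as the main summary. Amend SAP 5.2.7, 6.6.1 and 6.6.3 to add supplementary tables by arm, SOC and PT, covering onset through 90 days after the last dose:

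- SAEs, including fatal AEs, regardless of new anti-cancer therapy.
- Grade 3 or higher AEs, with non-serious events counted only up to the start of new therapy, to match what the protocol collects.

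For patients without new therapy, this brings the untabulated share for these events from 60/90 days to zero. The cost is a few extra tables from data already collected. The drawback is that some late events will reflect progression or subsequent treatment, so label the tables as supplementary and potentially confounded. Protocol Section 9 reports the final analysis as complete, so tables added now should also be marked as added after it.

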5.2.8. Standard derivations and reporting conventions

The following conversion factors will be used to convert days into weeks, months or years:
1 week = 7 days, 1 month = 30.4375 days, 1 year = 365.25 days.

Demographics and physical measurements:

- Age [years]:
 - (date of given informed consent - date of birth + 1) / 365.25
 - In case of missing day, day only: Age [years]: (year/month of given informed consent - year/month of birth)
 - In case only year of birth is given: Age [years]: (year of given informed consent - year of birth)

The integer part of the calculated age will be used for reporting purposes.

- BMI (kg/m²) = weight (kg)/[height (m)]²
- BSA (m²) = ([height (cm) × weight (kg)] / 3600)^{0.5}

For reporting conventions, mean and median should generally be displayed one more decimal place than the raw data and standard deviation should be displayed to two more decimal places than the raw data. Percentages will be reported to one decimal place. The rounding will be performed to closest integer / first decimal using the common mid-point between the two consecutive values. Eg, 5.1 to 5.4 will be rounded to an integer of 5, and 5.5 to 5.9 will be rounded to an integer of 6.

5.2.9. Unscheduled visits

Generally, data collected at unscheduled visits will be included and analyzed for both safety and efficacy analyses in the same fashion as the data collected at scheduled visits except where otherwise noted in the sections that follow. Descriptive statistics (mean, SD, median, minimum, maximum, quartiles) by nominal visit or time point for safety endpoints such as laboratory measurements, ECGs and vital signs will include only data from scheduled visits.

5.2.10. Adequate baseline tumor assessment

Adequate baseline is defined using the following criteria:

- All baseline assessments must be within 28 days prior to and including the date of randomization.
- All documented lesions must have non-missing assessments (ie, non-missing measurements for target lesions and non-missing lesions assessment status at baseline for non-target lesions).

5.2.11. Adequate post-baseline tumor assessment

An adequate post-baseline assessment is defined as an assessment where a response of CR, PR, SD, non-CR/non-PD, or PD can be determined (see Section 6.2.2.3). Time points where the response is not evaluable (NE) or no assessment was performed will not be used for determining the censoring date.

5.3. Methods to Manage Missing Data

5.3.1. Missing data

Unless otherwise specified, all data will be evaluated as observed, and no imputation method for missing values will be used.

In all patient data listings imputed values will be presented. In all listings imputed information will be flagged.

Missing statistics, eg when they cannot be calculated, should be presented as 'ND' or 'NA'. For example, if N=1, the measure of variability (SD) cannot be computed and should be presented as 'ND' or 'NA'.

5.3.1.1. Pharmacokinetic concentrations

Concentrations Below the Limit of Quantification

For all calculations, figures and estimation of individual pharmacokinetic parameters, all concentrations assayed as below the level of quantification (BLQ) will be set to zero. In log-linear plots these values will not be represented. The BLQ values will be excluded from calculations of geometric means and their CIs. A statement similar to 'All values reported as BLQ have been replaced with zero' should be included as a footnote to the appropriate tables and figures.

Deviations, Missing Concentrations and Anomalous Values

In summary tables and plots of median profiles, concentrations will be set to missing if one of the following cases is true:

1. A concentration has been reported as ND (ie, not done) or NS (ie, no sample);

2. A deviation in sampling time is of sufficient concern or a concentration has been flagged as anomalous by the clinical pharmacologist.

Summary statistics will not be presented at a particular time point if more than 50% of the data are missing. For analysis of pharmacokinetic concentrations, no values will be imputed for missing data.

5.3.1.2. Pharmacokinetic parameters

Whether actual or nominal PK sampling time will be used for the derivation of PK parameters will be determined by the results of interim PK analyses. If a PK parameter cannot be derived from a patient's concentration data, the parameter will be coded as NC (ie, not calculated). NC values will not be generated beyond the day that a patient discontinues.

In summary tables, statistics will be calculated by setting NC values to missing. Statistics will not be presented for a particular treatment if more than 50% of the data are NC. For statistical analyses (ie, analysis of variance), PK parameters coded as NC will also be set to missing.

If an individual patient has a known biased estimate of a PK parameter (due for example to a deviation from the assigned dose level), this will be footnoted in summary tables and will not be included in the calculation of summary statistics or statistical analyses.

5.3.1.3. Biomarker Parameters: Unintentional Duplicate Data

If an individual patient has unintentionally duplicated observations for a specific biomarker analyte(s) the following procedure will occur:

- For continuous data, the duplicate data points will be averaged, and the average added to the database;
- For non-continuous data (eg, listing of genes identified), the study team will discuss which, if any record, to select for analysis. A flag will be added to the database indicating which record is selected (including no record selected.)

For biomarker analytes for which it is intentional to have 2 samples (eg, denovo and archival tumor sample), these two samples will not be considered to be duplicate of each other, however, a variable in the database will identify the records.

5.3.2. Handling of incomplete dates

5.3.2.1. Disease history

Incomplete dates for disease history (eg, initial diagnosis date, date of documented, locally advanced, inoperable or metastatic disease diagnosis, date of response or progression in prior treatment) will be imputed as follows:

- If the day is missing, it will be imputed to the 15th day of the month.
- If both day and month are missing and the year is prior to the year of the first study treatment, the month and day will be imputed as July 1st.

- If both day and month are missing and the year is same as the year of the first study treatment, the month and day will be imputed as January 1st.
- If the date is completely missing, no imputation will be performed.

